## 7. STUDY POPULATION

### 7.1. Subjects Disposition

A disposition summary includes the number and percentage of patients in all analysis populations in the following categories:

#### Disposition - Year 1

- Per-protocol Population – Year 1
- Completed treatment through Week 48
- Discontinued treatment prior to Week 48
  - reason for discontinuing treatment
- Completed study follow-up through Week 52
  - on-treatment
  - discontinued treatment early but completed in-person study visits
  - continued to Year 2 follow-up
- Terminated from the trial before Week 52
- Follow-up by Year 1 study week
  - discontinued treatment
  - follow-up in-clinic
  - follow-up phone

#### Disposition - Year 2

- Per-protocol Population – Year 2
- Received at least one dose in Year 2
- Completed treatment through Week 100
- Discontinued treatment prior to Week 100
  - reason for discontinuing treatment
- Completed study follow-up through Week 104
  - on-treatment
  - discontinued treatment early but completed study visits
- Terminated from the trial before Week 104
- Follow-up by Year 2 study week

- discontinued treatment
- follow-up in-clinic
- follow-up phone

Patients who completed follow-up are defined as those who were followed by phone or in-person through the Week 104 visit. A listing of disposition is provided for all enrolled patients.

## 7.2. Screen Failures

Screen failures are not summarized.

## 7.3. Protocol Deviations

Prior to database lock at Year 1, a blinded team will perform a blinded data review to identify all deviations, including major protocol deviations that could potentially affect the efficacy conclusions of the study, to define the Per-Protocol population (see Section 6.3.2 and Section 6.3.3). A blinded team will repeat the blinded data review process for Year 2 deviations prior to the Year 2 database lock. Protocol deviations for excluded medications, patients who entered the study even though they did not satisfy all entry criteria, patients who received the wrong treatment or incorrect dose, and major protocol deviations are listed.

## 7.4. Demographic and Baseline Characteristics

Summaries of demographic and other baseline characteristic data are presented by treatment group for all analysis populations. They may also be summarized by select subgroups (including US and non-US) as appropriate (Section 8.3).

The demographic and other baseline characteristics include:

- Baseline Age, Age category (< 18, ≥ 18)
- Sex, Race, Ethnicity
- Weight (kg), Height (cm), BMI (kg/m^2)
- Diastolic and systolic blood pressure (mmHg), Heart rate (bpm)
- Serum creatinine, eGFR, eGFR categorical status (< 60, ≥ 60)
- ACR, ACR categorical status (≤ 300; > 300), ACR Stratum
- Prognosis of CKD by eGFR and Albuminuria categories
- Hematuria (present/absent)
- Angiotensin converting enzyme (ACE)-inhibitor treatment and/or Angiotensin II receptor blocker (ARB) (yes/no)
- Other baseline variables of interest

Alport syndrome related information includes:

- Age at Alport syndrome diagnosis

- Genetic subtype (x-linked, autosomal, unknown)
- Genotype (COL4A3, COL4A4, COL4A5, Unknown)
- Confirmed histologic diagnosis
- Hearing loss (yes/no)
- Visual impairment (yes/no)

## **7.5. Listing of Subject Inclusion and Exclusion Criteria**

A listing of enrolled patients who did not meet inclusion or exclusion criteria is generated.

## **7.6. Medical History**

Medical history is summarized by treatment. Medical history is coded using MedDRA (Medical Dictionary for Regulatory Activities) version 19.1. Medical history items are summarized by MedDRA SOC and PT.

### **7.6.1. Historical eGFR**

To characterize disease progression prior to trial entry, up to 5 years of historical serum creatinine values are collected for each patient as part of their medical history. Collection of historical serum creatinine is subject to availability of data from medical records; therefore, the number of available values will vary by patient and some patients may have no historical values. Historical serum creatinine values are converted to mg/dL and eGFR are calculated for analysis according to the appropriate equation (Section 6.5.6) using the patient age at laboratory collection for adult patients, or patient height at Screening for pediatric patients. Historical serum creatinine values were analyzed at various local laboratories (i.e., not collected as part of central lab data). Therefore, historical serum creatinine and corresponding eGFR values are considered part of a patient's medical history, and distinct from central lab assessments collected as part of the trial.

The eGFR values used in the analysis dataset for the baseline label are the baseline eGFR values for each patient (defined in Section 6.4.1), not the individual Screen A, Screen B, and Day 1 eGFR values.

Historical values are prior to first dose and have a negative Study Day value:

- Study Day = (Date of Historical Lab Collection) – (Date of Screen A)

Summary statistics of available historical eGFR results are based on the following analysis windows:

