### 6.5.6. Estimated Glomerular Filtration Rate (eGFR)

The eGFR is calculated using the formula below according to patient's age at the date of consent. The formula will not change throughout the study. The Chronic Kidney Disease Epidemiology Collaboration (CKD-EPI) equation is used for adult patients (age at consent at least 18 years):

- $eGFR \text{ (mL/min/1.73 m}^2\text{)} = 141 \times \min(S_{cr}/\kappa, 1)^\alpha \times \max(S_{cr}/\kappa, 1)^{-1.209} \times 0.993^{\text{Age}} \times 1.018 \text{ [if female]} \times 1.159 \text{ [if black]}$

The Bedside Schwartz equation is used for pediatric patients (age at consent of 12 to 17):

- $eGFR \text{ (mL/min/1.73 m}^2\text{)} = (0.41 \times \text{Height in cm}) / S_{cr}$

where  $S_{cr}$  is serum creatinine (mg/dL),  $\kappa$  is 0.7 for females or 0.9 for males, and  $\alpha$  is -0.329 for females or -0.411 for males. Min indicates the minimum of  $S_{cr}/\kappa$  and 1, and max indicates the maximum of  $S_{cr}/\kappa$  and 1. *Age* indicates age at time of serum creatinine collection. *Height* indicates height at time of serum creatinine collection.

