**Table 7. Labels for Summary of Historical Change in eGFR**

Analysis Visit	Label	Study Day Windows
-5	Historical Year 5	1825 to 1461 days prior to Screen A
-4	Historical Year 4	1460 to 1096 days prior to Screen A
-3	Historical Year 3	1095 to 731 days prior to Screen A
-2	Historical Year 2	730 to 366 days prior to Screen A
-1	Historical Year 1	365 to 1 days prior to Screen A
0	Baseline	Screen A to Day 1

The summary statistics will include the average eGFR value by patient and analysis time point. For instance, if multiple values are listed in the historical Year 1 results for a given patient, the average of those values is used to calculate the summary statistics.

Summary statistics of eGFR results by historical year (listed in Table 7) will also be summarized.

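### Historical paediatric eGFR is computed with Screening height, which inflates past values in patients who were still growing and creates or steepens an apparent pre-trial decline

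*SAP*

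**What the plan says.** SAP Section 7.6.1 gives the purpose of the summary: "To characterize disease progression prior to trial entry, up to 5 years of historical serum creatinine values are collected for each patient". It takes the equation from Section 6.5.6. For adults it uses age at each historical laboratory date. For paediatric patients it uses a single fixed input: "or patient height at Screening for pediatric patients".

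Section 6.5.6 assigns the Bedside Schwartz equation, 0.41 × height / serum creatinine, to patients aged 12 to 17 at consent. It says that height "indicates height at time of serum creatinine collection". The equation is chosen by age at consent and then kept: "The formula will not change throughout the study".

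Table 7 groups the historical values into yearly windows. The oldest, Historical Year 5, covers "1825 to 1461 days prior to Screen A". The series ends at the trial baseline: "The eGFR values used in the analysis dataset for the baseline label are the baseline eGFR values for each patient". Under Section 6.4.1 that baseline is built from screening and Day 1 measurements. Neither Section 7.6.1 nor Table 7 specifies a split by age.

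**The concern.** A patient aged 12 at consent may contribute creatinine drawn at about age 7 (12 − 5). Pairing that creatinine with the height measured at Screening applies a later, greater height to an earlier sample. The error goes one way for anyone who grew, gets larger the further back the sample lies, and almost vanishes at baseline. A growing child with perfectly stable kidney function would therefore appear to decline.

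What is at stake is the description of progression before entry, which is the stated reason for collecting these data. The bias is systematic, so averaging over more values or more patients does not remove it. The SAP does not mention its direction and plans no sensitivity summary.

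**Working it through.** The SAP gives no figure on this point to reproduce. The check is algebra on the Section 6.5.6 formula, followed by assumed ranges where the documents are silent.

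**Inputs from the SAP**
- Paediatric eGFR = 0.41 × height (cm) / serum creatinine (Section 6.5.6).
- Historical height = Screening height (Section 7.6.1).
- Oldest window = 1825 to 1461 days before Screen A (Table 7). Its midpoint is (1825 + 1461)/2 = 1643 days, about 4.5 years.

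**Assumed, because the documents do not give them**
- Screening height 160 cm.
- True eGFR constant at 60 mL/min/1.73 m².
- Growth since the sample of 0 to 30 cm.
- Paediatric share of patients with historical values of 5 to 25%.

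**Step 1: bias factor.** For a given past creatinine, the constant 0.41 and the creatinine cancel:

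eGFR(Screening height) / eGFR(height at sampling) = Screening height / height at sampling.

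This exceeds 1 whenever the patient grew, whatever the creatinine.

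**Step 2: one patient, sample about 4.5 years before entry.** Reported value = 60 × 160 / (160 − growth). Spurious slope = (60 − reported value) / 4.5.

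| Growth (cm) | Reported eGFR | Inflation | Spurious slope per year |
|---|---|---|---|
| 0 | 60.0 | 0% | 0 |
| 10 | 60 × 160/150 = 64.0 | 6.7% | -0.9 |
| 20 | 60 × 160/140 = 68.6 | 14.3% | -1.9 |
| 30 | 60 × 160/130 = 73.8 | 23.1% | -3.1 |

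With height at sampling, as Section 6.5.6 defines it, every row would read 60 with slope 0.

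**Step 3: shape across the Table 7 windows.** With steady growth, the value at each window midpoint is 60 × 160 / (160 − annual growth × years before Screen A).

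| Growth per year | Year 1 | Year 2 | Year 3 | Year 4 | Year 5 |
|---|---|---|---|---|---|
| 4 cm | 60.8 | 62.3 | 64.0 | 65.8 | 67.6 |
| 6 cm | 61.1 | 63.6 | 66.2 | 69.1 | 72.2 |

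The true value is 60 in every cell.

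**Step 4: dilution if adults and under-18s are summarised together.** Rise in the oldest-window mean = paediatric share × 60 × (160/(160 − growth) − 1).
- Share 5%, growth 10 cm: 0.05 × 4.0 = 0.2.
- Share 25%, growth 30 cm: 0.25 × 13.8 = 3.5.

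**Step 5: reach.** The models in Sections 8.6.1, 8.7.1, 8.8.1 and 8.9.1 adjust for baseline eGFR as defined in Section 6.4.1, not for historical eGFR. The testing sequence in Section 8.4 contains no historical measure. The sample size in Section 4.3 does not use one.

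**The case against.** The strongest reply is that Section 7.6.1 states a deliberate convention. It cites Section 6.5.6 for the equation and then names the input for one particular source: medical-record creatinine from local laboratories, kept distinct from the trial's central laboratory data. A specific rule ordinarily displaces a general one. A reader might infer that the two sections simply contradict each other by oversight; the text does not support that. What does stand is that the convention yields a biased result, and the SAP neither calls it a departure nor gives its direction.

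Past heights may also not exist. Section 7.6.1 mentions collecting creatinine only, and height first appears at Screen A in the schedule of assessments. The documents do not settle whether earlier heights are recorded. This objection stands, and it rules out simply dropping values that lack a sample-date height, which could remove every patient under 18.

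Pooling with adults is inferred from the absence of an age split. Age below 18 is a defined subgroup in Section 8.3, and Section 7.4 allows baseline characteristics by subgroup, but neither expressly covers historical eGFR.

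Finally, a reader might set one child's drift of several mL/min/1.73 m² beside the 3.3 to 4.0 difference in Section 4.3 and infer a threat to the treatment comparison. The documents do not support that. Those figures are between-arm differences in change from baseline, and historical eGFR does not enter them.

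**Conclusion.** The point holds, as a minor one. The direction is certain for any paediatric patient who grew between the historical sample and Screening: past eGFR is overstated, most in the oldest windows, so a decline is created or a true one made steeper. Adults are unaffected, and adolescents who had stopped growing are nearly so.

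The size is conditional on growth and paediatric share, neither of which the documents give. Under the assumptions shown, it runs from 0 to about -3.1 mL/min/1.73 m² per year for an individual. For a pooled oldest-window mean it is about 0.2 to 3.5 mL/min/1.73 m² with growth of 10 to 30 cm. It would therefore be too strong to say that pre-trial progression is materially overstated for the trial population as a whole. The consequence is confined to the descriptive account of progression before entry; the Week 48, 52, 100 and 104 analyses, their power and type I error are untouched.

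**What to change.** Amend Section 7.6.1 and Table 7 as follows:

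- Use a height from about the date of the historical sample wherever one is recorded.
- Present adults (18 or over) and under-18s separately.
- Where only Screening height exists, keep the values but flag them as biased upward for past dates, and state that this departs from the height definition in Section 6.5.6.
- Do not base any statement about pre-trial progression on a pooled figure that includes Screening-height values.

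The cost is SAP wording and smaller groups in a descriptive table. No endpoint, model, sample size or significance level changes.

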**Table 7. Labels for Summary of Historical Change in eGFR**

Analysis Visit	Label	Study Day Windows
-5	Historical Year 5	1825 to 1461 days prior to Screen A
-4	Historical Year 4	1460 to 1096 days prior to Screen A
-3	Historical Year 3	1095 to 731 days prior to Screen A
-2	Historical Year 2	730 to 366 days prior to Screen A
-1	Historical Year 1	365 to 1 days prior to Screen A
0	Baseline	Screen A to Day 1

The summary statistics will include the average eGFR value by patient and analysis time point. For instance, if multiple values are listed in the historical Year 1 results for a given patient, the average of those values is used to calculate the summary statistics.

Summary statistics of eGFR results by historical year (listed in Table 7) will also be summarized.

## 8. PRIMARY EFFICACY

Analyses of efficacy described in this section are the primary analyses of the Phase 3 efficacy endpoints, and pertain to the ITT population (i.e., all patients randomized in the Phase 3 portion of the study). The trial includes endpoints following one and two years of treatment. Additional details regarding the statistical approach and pseudo SAS code are available in the programming conventions document.

The following abbreviations are used in descriptions of the analysis models:

**Table 8. Model Parameter Abbreviations**

Abbreviation	Model Term
ACR_STRAT	ACR strata used in randomization
BASE_eGFR	Baseline eGFR
BASE_eGFR x VISIT	the interaction between baseline eGFR and time
TRT	treatment group
TRT_EXP1_	fraction of one-year exposure to treatment (Section 6.5.11)
TRT_EXP2	fraction of two-year exposure to treatment (Section 6.5.11)
TRT x VISIT	the interaction between treatment and time
VISIT	analysis visit used as time

### 8.1. General Considerations

Analyses are performed for all bardoxolone methyl patients in comparison with all placebo patients. Summary statistics for observed values, change from baseline, and percent change from baseline are presented by randomized treatment group. Missing values are imputed as described in Section 8.5.

### 8.2. Statement of the Null and Alternate Hypotheses

All primary and key secondary efficacy endpoints compare the change from baseline in eGFR for patients randomized to bardoxolone methyl ( $\mu_{\text{BARD}}$ ) to the change from baseline in eGFR for patients randomized to placebo ( $\mu_{\text{placebo}}$ ) at the endpoint-specified visit according to the following hypotheses:

- $H_0: (\mu_{\text{BARD}}) - (\mu_{\text{placebo}}) = 0 \text{ mL/min/1.73 m}^2$
- $H_1: (\mu_{\text{BARD}}) - (\mu_{\text{placebo}}) \neq 0 \text{ mL/min/1.73 m}^2$

Because eGFR decreases with disease progression, an increase in eGFR relative to placebo is considered evidence of benefit.

### 8.3. Subgroup Analyses

The primary and key secondary efficacy endpoints are analyzed for subgroups of interest to assess homogeneity of the effect size for those subgroups that are sufficiently large to warrant these analyses. Exploratory endpoints are also analyzed for these subgroups.

The following subgroup analyses are tabulated:

- Age (years):  $< 18$ ;  $\geq 18$
- Sex: female; male
- Geographic location: US; Non-US
- Ethnicity: Non-Hispanic/Latino; Hispanic/Latino
- Race: White; Non-White
- Baseline BMI ( $\text{kg}/\text{m}^2$ ):  $< 30$ ;  $\geq 30$
- Baseline eGFR ( $\text{mL}/\text{min}/1.73 \text{ m}^2$ ):  $\leq 60$ ;  $> 60$
- Baseline ACR ( $\text{mg}/\text{g}$ ):  $\leq 300$ ;  $> 300$
- Baseline ACEi/ARB use: Yes; No
- Genetic subtype: X-linked Alport syndrome (XLAS); Non-XLAS

Subgroup analyses will include nominal significance levels for descriptive purposes only. Forest plots are generated for change from baseline eGFR results in each subgroup at Weeks 48, 52, 100, and 104.

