### 2.1. Trial Rationale

Conceptually, this trial was designed to test the biological hypothesis that bardoxolone methyl slows disease progression in patients with Alport syndrome, as measured by changes in eGFR. Since on-treatment changes in eGFR may include both reversible, pharmacodynamic effects, as well as irreversible structural effects, analysis of eGFR after withdrawal is used to determine if bardoxolone methyl affects disease progression.

The presence of a sustained eGFR improvement after withdrawal of drug may be indicative of disease-modifying activity. In contrast, a decline in kidney function relative to placebo after drug withdrawal would be unlikely to provide a long-term benefit and could indicate the drug has harmed the kidney.

If the withdrawal analysis indicates that bardoxolone methyl improves kidney function relative to placebo, then this would suggest that the drug is likely to reduce underlying progression of the disease. It would also suggest that the on-treatment eGFR change would likely translate into a long-term renal benefit. Further, in routine clinical practice, physicians are unlikely to withdraw the drug, and an important element of the trial is to characterize the on-treatment eGFR change.

Analytically, the main intent of the trial is to characterize the change from baseline in eGFR following a 4-week withdrawal period. Within the two-year duration, there are two opportunities to test this biological hypothesis and determine if the change from baseline in eGFR is statistically significant relative to placebo. If the off-treatment change from baseline in eGFR is not statistically significant relative to placebo at Year 1, the trial design and analysis plan allow for an additional comparison of the off-treatment effect relative to placebo at Year 2.

Beyond the main intent of the trial, the trial is designed to also determine the following:

- The clinical benefit of bardoxolone methyl while receiving treatment, as measured by the on-treatment assessment of eGFR.
- Whether a treatment effect is observed over a period of up to two years.
- Whether a treatment effect trend is seen across various subgroups, such as stages of disease (i.e., across a spectrum of baseline eGFRs) and the pediatric population.

This document describes the analyses of protocol-specified endpoints to assess the effects of bardoxolone methyl on disease progression in patients with Alport syndrome.

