#### 4.3.1. Primary Endpoints

With 157 patients enrolled (78 in one group and 79 in the second group), the study will have approximately 80% power to detect a difference between the two treatment groups in change from baseline in eGFR of 3.4 mL/min/1.73 m^2 for the primary endpoint at Week 48 in Year 1. The power calculation for Year 1, which was based on mixed-model repeated measures (MMRM) analysis, assumes the following:

- 9 repeated measurements (Weeks 1, 2, 4, 6, 8, 12, 24, 36, and 48) having compound symmetry covariance structure
- The correlation between observations on the same subject is 0.7
- Two-sided Type I error rate of 0.025
- Standard deviation of change from baseline in eGFR of 8 mL/min/1.73 m^2
- Analyses at Week 48 are based on the intent-to-treat (ITT) population

Analysis of the Year 2 primary endpoint, which also will use the ITT population, will have approximately 80% power to detect a difference of 3.3 mL/min/1.73 m^2 assuming 13 repeated measurements, a correlation of 0.7 between observations, a standard deviation of 8 mL/min/1.73 m^2, and a two-sided type I error rate of 0.025. The primary analysis of efficacy will use an unstructured covariance structure, which is expected to have approximately the same power as the analysis with compound symmetry used for study planning.

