### **6.1. General Summary Table and Individual Subject Data Listing Considerations**

Results of statistical analyses are reported using summary tables, listings, and figures (TLFs). All TLFs will use ICH numbering conventions. The strategy for controlling the overall Type I error rate for the Year 1 and Year 2 primary and key secondary efficacy endpoints and other select exploratory endpoints is described in Section 8.4. For endpoints not described in Section 8.4, the reported significance levels are nominal and the following statistical conventions are used:

- Unless otherwise noted, all statistical testing is two-sided and is performed at the 0.05 significance level.
- Tests are declared statistically significant if the calculated p-value is  $<0.05$ .

All analyses and summaries are produced using SAS® version 9.3 (or higher).

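### SAP 8.3 sets out to assess homogeneity of effect across ten subgroup factors but specifies no between-level estimate of the difference in effect

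*SAP*

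**What the plan says.** SAP 8.3 states the purpose: "The primary and key secondary efficacy endpoints are analyzed for subgroups of interest to assess homogeneity of the effect size". It limits the work to subgroups large enough to justify it, without giving a size. Ten two-level factors follow: age, sex, geographic location, ethnicity, race, BMI, baseline eGFR, baseline ACR, ACEi/ARB use and genetic subtype.

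The planned outputs are tables, p-values and plots. On the p-values: "Subgroup analyses will include nominal significance levels for descriptive purposes only". On the plots: "Forest plots are generated for change from baseline eGFR results in each subgroup at Weeks 48, 52, 100, and 104".

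SAP 2.1 lists a related aim, naming disease stage and the pediatric population as examples: "Whether a treatment effect trend is seen across various subgroups".

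The only interactions in the MMRM of SAP 8.6.1, which 8.8.1 carries over, are treatment by visit and baseline eGFR by visit. The ANCOVA of 8.7.1 and 8.9.1 has none. The SAP addendum (4.4.2) adds region as a covariate for Weeks 100 and 104, but no treatment-by-region term.

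**The concern.** Homogeneity is a question about the difference in treatment effect between levels of a factor. Section 8.3 names no estimate of that difference, no interval for it and no criterion for judging it. Read with the hypotheses of 8.2 and the models of 8.6 to 8.9, its nominal p-value tests for zero effect within a level.

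That p-value depends heavily on how many patients the level contains. With 157 patients in all, the smaller level of an unbalanced factor has low power. A result that is significant in one level and not in the other can then be taken for effect modification when it reflects only subgroup size. What is at stake is the interpretation of exploratory results, for example adults against adolescents or ACR up to 300 against above 300.

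**Working it through.** **Inputs from the SAP.** N = 157, in arms of 78 and 79 (4.3.1). SD of change 8, and for the key secondary endpoint 80% power at a difference of 4.0 and 50% at 2.9, two-sided alpha 0.025 (4.3.2). Outside the 8.4 sequence, "all statistical testing is two-sided and is performed at the 0.05 significance level" (6.1). Patients with ACR above 300 at the Screen B visit make up no more than about 40% (4.4).

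**Assumed.** All other subgroup shares, taken as 10% to 50% because the documents give none. Also 1:1 allocation within each level, SD 8 in each level, no further gain from covariates, and levels treated as independent because they contain different patients.

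**Step 1: reproduce the SAP's power.** A two-sample t-test with 78 and 79 patients and SD 8 at 0.025 gives 80.7% at 4.0 and 50.4% at 2.9, matching 4.3.2. For the MMRM, the SD of a time-averaged change under compound symmetry is 8 × √[(1 + (m − 1) × 0.7)/m]. This is 6.85 for m = 9 and 6.80 for m = 13. Power by the normal approximation is then 80.7% at 3.4 and 78.7% at 3.3, close to the stated 80%.

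**Step 2: power within each level under one common effect of 4.0.** For a share f, each arm in that level has n = 157f/2 patients. The noncentrality is 4.0/[8 × √(2/n)], and power comes from the noncentral t distribution at two-sided 0.05. For f = 0.5, n = 39.25, the noncentrality is 2.22 and power is 0.590.

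**Step 3: chance that exactly one level is significant**, p₁(1 − p₂) + p₂(1 − p₁):

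| Split | Power, smaller level | Power, larger level | Exactly one significant |
|---|---|---|---|
| 50:50 | 0.590 | 0.590 | 48% |
| 40:60 (ACR cap) | 0.496 | 0.670 | 50% |
| 30:70 | 0.390 | 0.738 | 55% |
| 20:80 | 0.273 | 0.794 | 63% |
| 10:90 | 0.152 | 0.839 | 74% |

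If all ten factors were analyzed at one visit, the expected number of discordant factors would be at least 10 × 0.48 = 4.8. Expectations add whether or not the factors are independent.

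**Step 4: dependence on the true effect.** Range from 50:50 to 10:90 splits at nominal 0.05:

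- effect 0: about 10% throughout
- effect 2.0: 31% to 34%
- effect 2.9: 46% to 56%
- effect 5: 34% to 77%
- effect 6: 17% to 72%
- effect 8: 2% to 55%

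**Step 5: what an interaction estimate would give.** With n₁ and n₂ patients per arm in the two levels, SE = 8 × √(2/n₁ + 2/n₂). At 50:50 this is 8 × √(2/39.25 + 2/39.25) = 2.55, so the 95% CI is ±1.96 × 2.55 = ±5.0. At 25:75 (n₁ = 19.6, n₂ = 58.9) the SE is 2.95 and the CI ±5.8. The difference in effects detectable with 80% power at 0.05 is (1.96 + 0.84) × SE, about 7.2 at 50:50 and 8.9 at 20:80 (SE 3.19). An interaction test gives a false signal in 5% of homogeneous factors whatever the effect or split. Over ten independent tests, the chance of at least one is 1 − 0.95¹⁰ = 40%.

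**The case against.** A reader might infer that the SAP plans to judge homogeneity by comparing significance between levels. It does not say so. Section 8.3 labels the p-values descriptive, names effect size as the target and plans forest plots, which put the estimates for the levels side by side. That is a common way to show consistency. This objection stands, so the discordance figures describe a misreading that the plan leaves open, not a rule that it sets.

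A reader might also infer that a homogeneous effect will look heterogeneous in half or more of the splits. That holds near the design effect and not in general, as Step 4 shows. The highest rates come from very unbalanced splits, and 8.3 restricts the analyses "to assess homogeneity of the effect size for those subgroups that are sufficiently large to warrant these analyses". No threshold is given, so the restriction may remove some of those splits but cannot be relied on to do so.

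A third inference is that SAP 2.1 makes homogeneity a trial aim. It asks whether an effect trend is seen across subgroups, and within-level estimates speak to that. The mismatch between aim and method lies in 8.3 alone.

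Two further points stand. Subgroup results carry no alpha and lie outside the testing sequence of 8.4. SAP 8 also refers to a programming conventions document, not available here, which could contain an interaction term. Even so, the measure of homogeneity belongs in the SAP that states it as the purpose.

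**Conclusion.** The gap is real but narrow. SAP 8.3 states homogeneity of effect size as its purpose, and neither the SAP nor its addendum specifies a between-level estimate or a criterion. The descriptive label limits what may be claimed from the p-values, but it does not turn a test against zero within a level into a comparison of levels.

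The size is conditional on significance being compared between levels and on the true effect. At the SAP's design value of 4.0 the chance of discordance is about half for balanced splits and for the ACR cap, and about three quarters at 10:90. In 50:50 splits it is far lower under no effect or a large one. The ACR cap is the only subgroup share in the documents, and it applies to screening ACR whereas the subgroup uses baseline ACR.

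The primary and key secondary conclusions are untouched. This is a cheap improvement to exploratory interpretation.

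**What to change.** In SAP 8.3, specify for each factor a treatment-by-subgroup interaction, with its lower-order terms, in the models of 8.6.1, 8.7.1, 8.8.1 and 8.9.1, fitted to all ITT patients. In the MMRM this is treatment by subgroup by visit. On the forest plots, report the between-level difference in treatment effect with its 95% CI and the nominal interaction p-value. State that within-subgroup p-values are not used to judge homogeneity.

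The cost is a sentence or two in 8.3 and one interaction per factor in models that already exist. The estimates will be imprecise: an interval of ±5.0 to ±5.8 is wider than the 4.0 design effect. The text should say that a non-significant interaction does not show homogeneity. With about a 40% chance of at least one false signal in ten independent tests, the interaction p-values should also stay descriptive.
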